3.2. Subject Selection

3.2.1. Inclusion Criteria

All subjects must satisfy the following criteria to be considered for study participation:

1. Is able to speak and understand the language in which the study is being conducted, is able to understand the procedures and study requirements, and has voluntarily signed and dated an informed consent form approved by an IRB before the conduct of any study procedures;
2. Is a male or female ≥ 18 and ≤ 65 years of age;
3. Is classified using the American Society of Anesthesiologists Physical Status Classification System as P1 to P2;
4. Has undergone primary, unilateral, distal first metatarsal bunionectomy (osteotomy and internal fixation) with no additional collateral procedures;
5. Experiences a pain intensity rating of ≥ 4 on an 11-point (0-10) Numeric Rating Scale (NRS) during the 9-hour period after discontinuation of the anesthetic block;
6. Has a body weight ≥ 45 kg and a body mass index (BMI) ≤ 40 kg/m²;
7. If female and of childbearing potential, is non-lactating and non-pregnant (has negative pregnancy test results at Screening [serum] and on Day 0 before surgery [urine]);
8. If female, is either not of childbearing potential (defined as postmenopausal for at least 1 year or surgically sterile [bilateral tubal ligation, bilateral oophorectomy, or hysterectomy]) or practicing 1 of the following medically acceptable methods of birth control:
 - a. Hormonal methods such as oral, implantable, injectable, vaginal ring, or transdermal contraceptives for a minimum of 1 full cycle (based on the subject's usual menstrual cycle period) before study drug administration
 - b. Total abstinence from sexual intercourse since the last menses before study drug administration
 - c. Intrauterine device
 - d. Double-barrier method (condoms, sponge, or diaphragm with spermicidal jellies or cream)

9. Is willing and able to comply with study requirements (including diet, alcohol, and smoking restrictions), complete the pain evaluations, remain at the study site for ≥ 72 hours, and return for a follow up visit 7 ± 2 days after surgery.

3.2.2. Exclusion Criteria

Subjects will be excluded for any of the following:

1. Has a known history of allergic reaction or clinically significant intolerance to acetaminophen, aspirin, opioids, or any nonsteroidal anti-inflammatory drugs (NSAIDs); history of NSAID-induced bronchospasm (subjects with the triad of asthma, nasal polyps, and chronic rhinitis are at greater risk for bronchospasm and should be considered carefully); or hypersensitivity, allergy, or significant reaction to sulfa (including sulfonamide) medicines, ingredients of the study drug, or any other drugs used in the study, including anesthetics and antibiotics that may be required on the day of surgery;
2. Has experienced any surgical complications or other issues that, in the investigator's opinion, could compromise the subject's safety if he or she continues into randomized treatment or could confound the results of the study;
3. Has a known or suspected history of alcoholism or drug abuse or misuse within 2 years of Screening or evidence of opioid tolerance or physical dependence before dosing with the study drug;
4. Is pregnant or breastfeeding;
5. Has any clinically significant unstable cardiac, respiratory, neurological, immunological, hematological, or renal disease, or any other condition that, in the investigator's opinion, could compromise the subject's welfare, ability to communicate with the study staff, or otherwise contraindicate study participation;
6. Has long QT Syndrome, a family history of long QT Syndrome, history of bradyarrhythmias or is taking Class IA or Class III antiarrhythmic medications;
7. Has any ongoing condition, other than one associated with the current primary, unilateral, first metatarsal bunionectomy, that could generate levels of pain sufficient to confound the results of the study (e.g., severe osteoarthritis of the target joint or target extremity, or other painful condition, in the opinion of the investigator, which contraindicates their participation); Has a history or current diagnosis of a significant psychiatric disorder that, in the investigator's opinion, would affect the subject's ability to comply with the study requirements (e.g., major depression, schizophrenia, or hallucinations);
8. Has tested positive either on the urine drug screen (Screening and/or Day 0) or on the alcohol Breathalyzer test (Day 0). Subjects who test positive at Screening only and can produce a prescription in their name from their physician for the medication producing the positive test may be considered for study enrollment at the investigator's discretion;
9. Has a history of a clinically significant (in the investigator's opinion) gastrointestinal (GI) event within 6 months before Screening or has any history of peptic or gastric ulcers or GI bleeding;

10. Has an active infection, mucositis, cold sores, viral lesions, local irritation, or periodontal disease of the oral cavity. In addition, has evidence of piercings of the tongue or anywhere in the oral cavity, has a history of oral cavity piercings, or has a history of significant dental disease;
11. Has a surgical or medical condition of the GI or renal system that, in the investigator's opinion, might significantly alter the absorption, distribution, or excretion of any drug substance;
12. Is considered by the investigator, for any reason (including, but not limited to, the risks described as precautions, warnings, and contraindications in the current version of the investigator's brochure for Fentanyl Sublingual Spray), to be an unsuitable candidate to receive the study drug;
13. Is receiving systemic chemotherapy, has an active malignancy of any type, or has been diagnosed with cancer within 5 years before Screening (excluding squamous or basal cell carcinoma of the skin);
14. Is currently receiving anticoagulants (e.g., heparin or warfarin). Low-dose aspirin for cardio protection is allowed;
15. Has used drugs with enzyme-inducing properties, such as rifampicin and St. John's Wort, or any drug known to be a strong inhibitor or inducer of CYP3A4 within 3 weeks before surgery;
16. Has received a course of systemic corticosteroids (either oral or parenteral) within 3 months before Screening (inhaled nasal steroids and topical corticosteroids are allowed);
17. Has received or will require any analgesic medication within 5 half-lives (or, if half-life is unknown, within 48 hours) before surgery;
18. Has a history of chronic use (defined as daily use for >2 weeks) of NSAIDs, opiates, or glucocorticoids (except inhaled nasal steroids and topical corticosteroids) within 6 months before study drug administration. Aspirin at a daily dose of ≤ 325 mg is allowed for cardiovascular prophylaxis if the subject has been on a stable dose regimen for ≥ 30 days before Screening and has not experienced any relevant medical problem. (NOTE: Subjects who were prescribed or instructed to use NSAIDs or other analgesics for >2 weeks following a surgical procedure or treatment of temporary acute pain/inflammation secondary to an injury are exempted from this exclusion provided the condition being treated is not chronic and the protocol-mandated washout period is observed);
19. Has been treated with agents that could affect the analgesic response (such as central alpha agents [clonidine and tizanidine], neuroleptic agents, and other antipsychotic agents) within 2 weeks before Surgical Period (Day 0).
20. Has used serotonergic drugs include selective serotonin reuptake inhibitors (SSRIs), serotonin and norepinephrine reuptake inhibitors (SNRIs), tricyclic antidepressants (TCAs), triptans, 5-HT₃ receptor antagonists, drugs that affect the serotonergic neurotransmitter system (e.g., mirtazapine, trazodone, tramadol), and drugs that impair metabolism of serotonin (including MAO inhibitors, both those intended to treat psychiatric disorders and also others, such as linezolid and intravenous methylene blue) within 2 weeks before Surgical Period (Day 0).

21. Has a significant renal or hepatic disease, as indicated by clinical laboratory assessment (results $\geq 3 \times$ the upper limit of normal [ULN] for any liver function test, including aspartate aminotransferase, alanine aminotransferase, and lactate dehydrogenase, or creatinine $\geq 1.5 \times$ ULN);
22. Has any clinically significant laboratory or 12-lead electrocardiogram finding at Screening that in the investigator's opinion contraindicates study participation;
23. Has screening systolic blood pressure ≥ 160 mmHg and diastolic blood pressure >100 mmHg (may be repeated 1 additional time after 5 minutes rest to verify). The investigator may, at his discretion, choose to exclude subjects with hypertensive levels lower than these if he deems it in the best interest of the subject;
24. Oxygen saturation (SpO₂) below 95% at screening;
25. Has a history or presence of postoperative vomiting (CTCAE guidelines for vomiting) grade 2 or higher, as a result of surgery and/or anesthesia. Has a history of sleep apnea, chronic obstructive pulmonary disease and any other obstructive airway disease requiring supplemental oxygen; or
26. Has significant difficulties swallowing capsules or is unable to tolerate oral medication.

3.3. Removal of Subjects from Therapy or Assessment

All subjects will be advised that they are free to withdraw from participation in this study at any time, for any reason, and without prejudice. Every reasonable attempt should be made by the investigator to keep subjects in the study. However, subjects must be withdrawn from the study if they withdraw consent to participate. Investigators must attempt to contact subjects who fail to attend scheduled visits by telephone or other means to exclude the possibility of an AE being the cause of withdrawal. Should this be the cause, the AE must be documented, reported, and followed as described in Section 6.2.6.8. The sponsor reserves the right to request the withdrawal of a subject due to protocol violations or other reasons.

The investigator also has the right to withdraw subjects from the study at any time for lack of therapeutic effect that is intolerable or otherwise unacceptable to the subject, for intolerable or unacceptable AEs, intercurrent illness, noncompliance with study procedures, administrative reasons, or in the investigator's opinion, to protect the subject's best interest.

If one of the following events occur during the Treatment Period, the subject will be discontinued from further study participation:

1. Hypoxia with oxygen saturation $\leq 90\%$ on repeat measurements over 3 minutes, despite stimulation and receiving oxygen 2-4 L/min via nasal cannula.
2. Hypoxia or respiratory depression requiring the use of naloxone for reversal.
3. Need for noninvasive respiratory maneuvers (eg, jaw thrust, bag-valve mask for positive pressure ventilation, etc.) to improve or maintain adequate respiratory status (ventilation and/or adequate oxygen saturation) at any point during the study.
4. Hypotension requiring intervention, as follows:
 - a. If asymptomatic and <80 mm Hg systolic blood pressure on 3 successive repeat measurements over a 15-minute period.

- b. If symptomatic, but >80 mm Hg systolic blood pressure and does not respond to conservative measures such as oral hydration and/or no more than 1 liter of IV fluids (if more than 1 liter of IV fluid is needed and/or if naloxone is administered, the subject will be discontinued from further dosing).

Oxygen saturation will be monitored continuously and the study team will measure all vital signs (blood pressure, heart rate, respiratory rate, and oxygen saturation) at least every 5 minutes until the AE of hypotension or hypoxia as described above is no longer present.

5. If >8 mg i.v. ondansetron is needed within an 8-hour segment and persistent nausea and/or emesis is present.
6. Pain cannot be adequately managed (in the investigator's opinion) by a combination of study drug and rescue medication, or who develop unacceptable side effects during the study, will be discontinued from further study participation.

Pain will be managed according to usual standard of care at the investigator's discretion.

If a subject is withdrawn before completing the study, the reason for withdrawal and the date of discontinuation will be recorded on the appropriate case report form (CRF). Whenever possible and reasonable, the evaluations that were to be conducted at the completion of the study should be performed at the time of premature discontinuation.

If a subject discontinues the study prematurely, pain intensity, pain relief, and the subject's global satisfaction with study treatment should be assessed and recorded immediately before discontinuation.

Withdrawn subjects will not be replaced. If a substantial number of subjects are withdrawn from the study, then the sponsor will evaluate the need for developing replacement criteria.

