During the Treatment Period subjects will be allowed to use assigned study medication for primary rescue medication no more frequently than 4 hours from previous study medication dose and no more than 6 times in a 24-hour period. Subjects will be encouraged to wait for at least 1 hour after the first dose of study drug before receiving rescue medication to allow time for the study drug to exert its pharmacologic effect.

During the Treatment Period, subjects whose pain cannot be adequately managed (in the investigator's opinion) by a combination of study drug and rescue medication, or who develop unacceptable side effects during the study, will be discontinued from further study participation. Their pain will be managed according to usual standard of care at the investigator's discretion.

Pain will be assessed on an 11-point Numeric Rating Scale (NRS) at Baseline before Time 0. Thereafter, subjects will rate their pain intensity (NRS) and pain relief (on a 5-point categorical scale) and record their assessments in an inpatient subject diary at scheduled times during the 48-hour period after Time 0 (at 2.5, 5, 15, 30, and 45 minutes, and 1, 1.5, 2, 3, 4, 5, 6, 7, 8, 12, 16, 20, 24, 32, 40, and 48 hours) and immediately before each use of rescue analgesia during the Treatment Period. Time to perceptible pain relief and meaningful pain relief will be evaluated using the 2 stopwatch method (after the first dose only). Time to each rescue medication from the prior IP dose will be evaluated. Subjects will complete a subject's global evaluation of the study drug at the end of the Treatment Period (Day 3) before discharge from the study site.

If a subject discontinues the study prematurely, pain intensity, pain relief, and the subject's global satisfaction with study treatment should be assessed and recorded immediately before discontinuation.

Before discharge from the study site on Day 3, study personnel will dispense a prescription for outpatient pain medication (if not already dispensed) and subjects will be given an outpatient subject diary in which they will be instructed to record concomitant medications taken and adverse events (AEs) experienced after discharge. Subjects will also be instructed to return the outpatient subject diary to study personnel at the Follow-up Visit on Day 7 \pm 2 days (5 to 9 days after surgery).

Number of subjects (planned):

Approximately 45 subjects (15 subjects per treatment group) will be enrolled.

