Pain will be assessed on an 11-point Numeric Rating Scale (NRS) at Baseline before Time 0. Thereafter, subjects will rate their pain intensity (NRS) and pain relief (on a 5-point categorical scale) and record their assessments in an inpatient subject diary at scheduled times during the 48-hour period after Time 0 (at 2.5, 5, 15, 30, and 45 minutes, and 1, 1.5, 2, 3, 4, 5, 6, 7, 8, 12, 16, 20, 24, 32, 40, and 48 hours) and immediately before each use of each rescue analgesia during the Treatment Period. Time to perceptible and meaningful pain relief will be evaluated using the 2 stopwatch method (after the first dose only). Subjects will complete a subject's global evaluation of the study drug at the end of the Treatment Period (Day 3) before discharge from the study site.

[figure not shown]
If a subject discontinues the study prematurely, pain intensity, pain relief, and the subject's global satisfaction with study treatment should be assessed and recorded immediately before discontinuation.

Before discharge from the study site on Day 3, study personnel will dispense a prescription for outpatient pain medication (if not already dispensed) and subjects will be given an outpatient subject diary in which they will be instructed to record concomitant medications taken and adverse events (AEs) experienced after discharge. Subjects will also be instructed to return the outpatient subject diary to study personnel at the Follow up Visit, 7 ± 2 days after surgery.

The planned sequence and maximum duration of the study periods will be as follows:

- Screening Period: up to 28 days
- Surgical Period: Day 0
- Treatment Period: Days 1-3 (up to 9 hours post-surgery plus 48 hours of treatment and inpatient assessments)
- Follow-up: Day 7 ± 2 days (5 to 9 days after surgery) or early withdrawal

Subjects will be confined for approximately 72 hours at the study site for the Surgical and Treatment Periods. The maximum study duration for each subject is approximately 6 weeks

Figure 1: Study Design Schematic

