8.5.3.3. Sensitivity Analyses

Sensitivity analyses to explore the impact of missing data and use of rescue will be performed for the primary efficacy analysis. Specifics of the sensitivity analyses will be described in the SAP.

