APPENDIX 5. RESCUE MEDICATION FOR POST-OPERATIVE NAUSEA AND/OR EMESIS (PONV, PROPOSED GUIDANCE)

1. Administer initial dose of ondansetron (Zofran®) 4 mg IV if nausea \geq 5 mins.
2. If symptoms are persistent, then a second dose of ondansetron 2mg IV may be administered in 15-60 minutes
3. If PONV continues to be a problem, an additional dose of ondansetron 2mg IV can be given after an additional 15-60 minutes. Do not administer more than 8 mg of ondansetron within an 8-hour period.
4. If vomiting persists at least 60 minutes following 8 mg IV ondansetron within an 8-hour period (i.e., patient is refractory to ondansetron) metoclopramide (Reglan®) may be administered for further treatment of persistent PONV.
5. Metoclopramide (Reglan®), 10-20 mg IM may be administered q4-6hr (max daily dose: 40 mg).
6. If PONV is not adequately controlled with metoclopramide, subject will be discontinued from the study.
7. PI should call Medical Monitor to discuss subjects with refractory PONV/emesis.

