7.3 Handling of Missing Data

7.3.1 Handling of Missing Data for Efficacy Assessments

Use of Rescue Medication: Any pain intensity or pain relief score occurring within 4 hours after a subject has taken rescue medication for pain will be replaced by the last pain intensity or pain relief score prior to that use of rescue medication. If a second rescue medication for pain is used within that 4 hour duration, the pain intensity or pain relief scores from the time of the first rescue medication will be replaced by the assessment prior to the second rescue medication for the next 4

hours. The same method will be employed for a third and subsequent rescue medication.

Missing due to Dropouts: Missing values for pain intensity after a subject drops out of the study will be imputed as follows in the primary analysis:

- For SPID endpoints, the last available SPID (truncated SPID) will be used for analysis (e.g., if a subject dropped out after 32 hours of initiation of treatment, the truncated SPID calculated using timepoints up to 32 hours will be used as the post 32 hour timepoints like 40 hours and 48 hours).
- For TOTPAR endpoints, the last available TOTPAR (truncated TOTPAR) will be used for analysis
- For PID endpoints, the last available pain intensity will be used to impute the missing pain intensity and to calculate the PID

In addition, a sensitivity analysis using 1) missing as missing (i.e., no imputation) for dropouts and 2) multiple imputation will be performed for the primary endpoint to explore the impact of missing data after a subject drops out. The details of the sensitivity analysis are described in [Section 7.4](#).

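### Protocol 3.3 ends study participation, not only dosing, so no planned SPID-48 analysis has observed pain scores after a removal

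*Protocol*

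**What the plan says.** Protocol 3.3 introduces its list of events with "If one of the following events occur during the Treatment Period, the subject will be discontinued from further study participation". The list covers hypoxia, naloxone reversal, respiratory manoeuvres, hypotension, persistent nausea or emesis despite ondansetron, uncontrolled pain and unacceptable side effects. The synopsis, Protocol 3.1 and SAP 2.2 repeat the rule for subjects whose pain cannot be managed "or who develop unacceptable side effects during the study, will be discontinued from further study participation". Appendix 5 item 6, which is guidance, adds: "If PONV is not adequately controlled with metoclopramide, subject will be discontinued from the study".

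For a removed subject, 3.3 says that pain intensity, pain relief and "global satisfaction with study treatment should be assessed and recorded immediately before discontinuation". Protocol 6.1.1, 6.1.2, 7.3.2 and Table 2 footnote k tie the extra rating to early withdrawal. None of them schedules a later rating up to 48 hours.

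Some wording points to drug-only stops. Item 4b of 3.3 says that "if naloxone is administered, the subject will be discontinued from further dosing". Protocol 6.2.6.3 has an action category for stopping study drug. SAP 8.2.4 tabulates adverse events that end treatment separately from those that end study participation.

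On analysis, SAP 7.3.1 says "Missing values for pain intensity after a subject drops out of the study will be imputed as follows in the primary analysis", and for SPID it carries the truncated sum forward. The last sentence of SAP 8.2.1 says that missing pain intensity is not imputed in the primary analysis. Protocol 8.5.3.3 promises: "Sensitivity analyses to explore the impact of missing data and use of rescue will be performed for the primary efficacy analysis". SAP 7.4 lists two analyses, missing-as-missing and multiple imputation, and both concern missing data.

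**The concern.** The efficacy population is all randomised subjects, the endpoint runs to 48 hours, and withdrawn subjects are not replaced. Several removal criteria could plausibly occur at different rates by arm. Respiratory events and vomiting resemble the opioid effects listed in Protocol 1.5, while uncontrolled pain may be more common on placebo. If scoring stops when the drug stops, the later scores are lost for good, whereas an analysis rule can still be changed before unblinding.

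What is at stake is one question that the trial then cannot answer from observed data: how much pain randomised subjects had over 48 hours under their assigned treatment followed by whatever care they needed. The two SAP defects are separate. One leaves it unclear whether a removed subject enters the primary analysis with a partial sum or not at all. The other leaves a promised analysis unspecified.

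**Working it through.** **What each SPID-48 analysis does with the hours after a stop**

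| Analysis | Post-stop hours |
|---|---|
| Primary, SAP 7.3.1 | The truncated sum stands as SPID-48. Under the 7.9.7 formula this counts each later hour as zero change from baseline |
| Primary if SAP 8.2.1 governs; also 7.4.1 | Subject left out, or later terms dropped from the sum (the same value as truncation), depending on reading. The two analyses coincide |
| Multiple imputation, SAP 7.4.2 | Modelled from treatment, site, baseline and SPID by time point, with no observed post-stop data |
| Per-protocol, SAP 6.2 | Subject left out |

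No row uses an observed score after removal.

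**Share of the window unobserved.** For a stop at t hours this is (48 − t)/48. The stop times are assumptions.
- t = 8: 40/48 = 83%. Seven of the 21 scheduled post-dose time points are lost (12, 16, 20, 24, 32, 40, 48 h).
- t = 24: 24/48 = 50%. Three time points are lost (32, 40, 48 h).

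**How far the primary depends on its dropout rule.** Let c be baseline NRS minus last NRS. Counting the remaining hours as zero rather than at the last level changes a subject's SPID-48 by (48 − t)c. With c assumed from −2 (worse than baseline) to +3:
- t = 8: 40 × (−2) = −80 to 40 × 3 = +120.
- t = 24: 24 × (−2) = −48 to 24 × 3 = +72.

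On a 15-subject arm mean, k subjects stopping at 8 h contribute k × 40c/15:
- k = 1: −80/15 = −5.3 to 120/15 = +8.0.
- k = 3: −16 to +24.

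With the synopsis SD of 100 and no covariate gain, the SE of an arm difference is 100 × √(2/15) = 36.5. The k = 3 range is then −16/36.5 = −0.44 to 24/36.5 = +0.66 SE. This takes all three stops at 8 h with the same c and none in the comparator arm.

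**Complete-case reading of 8.2.1 only.**
- One arm loses 3 of 15: SE = 100 × √(1/12 + 1/15) = 38.7 (+6%).
- Both arms lose 3: SE = 100 × √(2/12) = 40.8 (+12%).

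These last two calculations compare dropout rules. Collecting more ratings does not change them; choosing one rule settles the second.

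**Plan's own figures.** The documents give no removal rate, so there is no plan figure to reproduce on this point. The fix leaves the planned 15 per arm and the stated power untouched.

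**The case against.** The strongest case against is that this is a preference. The primary objective is analgesic efficacy against placebo, and the 4-hour rescue rule in SAP 7.3.1 tries to remove the effect of other analgesics. No objective asks for pain under assigned treatment followed by usual care. Post-stop scores include standard-of-care analgesia, so a subject who fails on pain and is then well treated will look improved. An amendment to a 45-subject Phase 2 trial for one extra analysis could be called optional. Much of this stands, and it is why the post-stop scores belong in one labelled sensitivity analysis and why the recommendation is a low one. It does not remove the gap: the scores cost little while subjects are inpatients, and they cannot be recovered later.

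A reader might infer more than the documents support:
- **That the plan biases the result for or against fentanyl.** Removal for side effects and removal for pain could pull in opposite directions, and no rates are given.
- **That −0.44 to +0.66 SE is a bias estimate.** It is the distance between two imputation rules under assumed stops.
- **That drug-only stops are ruled out everywhere.** Item 4b, the action category in 6.2.6.3 and the tabulations in SAP 8.2.4 allow for them, and 3.3 tells investigators to try to keep subjects in the study. What is missing is a procedure.
- **That post-stop scores would validate the multiple imputation.** They answer a different question.

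**Conclusion.** The concern holds in a limited form. On the listed events Protocol 3.3 takes subjects out of the study and schedules no pain score from then to 48 hours. All planned SPID-48 analyses therefore truncate, omit or model those hours, and none can describe pain to 48 hours in all randomised subjects under assigned treatment followed by usual care. The only measure of that gap is the unobserved share, 83% or 50% of the window at assumed stops of 8 or 24 hours. The number of subjects affected, and the size and direction of any bias, cannot be derived from the documents.

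Two textual defects hold independently of any assumption: the 7.3.1/8.2.1 conflict, and the missing rescue-use sensitivity analysis. Both can be repaired in the SAP alone, and they should not add weight to the design point. Overall the plan should be changed, at the low end of that grade, given a small Phase 2 trial with no stated removal rate.

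**What to change.** 1. **Protocol.** Keep every criterion in 3.3, but state that it stops study drug only. Unless the subject withdraws consent, leaves the site or is clinically unable, continue the scheduled NRS and pain-relief ratings and the recording of analgesics to 48 hours. Make matching edits in the synopsis, 3.1, 6.1.1, 6.1.2, 7.3.2, Table 2 footnote k, Appendix 5 item 6 and SAP 2.2.
2. **One primary rule.** Delete the last sentence of SAP 8.2.1 so that 7.3.1 governs, and apply 7.3.1 from permanent study-drug stop as well as from dropout. Exclude post-stop scores from the primary, 7.4.1, 7.4.2 and the secondary endpoints, with matching censoring edits in 7.9.11 to 7.9.17. Define the per-protocol set (synopsis, Protocol 8.4, SAP 6.2) as 48 hours on study treatment.
3. **Two separate sensitivity analyses in SAP 7.4.**
   - (a) Rescue use: the primary rule without the 4-hour rescue replacement. This needs no new data and meets the promise in Protocol 8.5.3.3.
   - (b) Treatment policy: all recorded scores to 48 hours as observed, with scores still missing handled by the 7.4.2 multiple imputation. Label it as assigned treatment followed by rescue and standard-of-care analgesia.

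**Cost.** A protocol amendment and the SAP edits above. The ratings are already on the schedule, and the plan says "Subjects will be confined for approximately 72 hours at the study site for the Surgical and Treatment Periods". A stop at 8 hours adds 7 × 2 = 14 ratings, and a stop at 24 hours adds 3 × 2 = 6. If 3 per arm stopped at 8 hours (assumed), that is 9 × 14 = 126 of 45 × 21 × 2 = 1,890 scheduled post-dose ratings, or 6.7%. Staff must also keep rating subjects who may be unwell, some of whom will leave. The post-stop scores serve analysis (b) only.
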